7.2.2.2 Imputation rules for missing or partial medication start/stop dates

Missing or partial medication start date:

- If only Day is missing, use the first day of the month.
- If Day and Month are both missing, use the first day of the year.
- If Day, Month and Year are all missing, use a date before the first dose date.

Missing or partial medication stop date:

- If only Day is missing, use the last day of the month.
- If Day and Month are both missing, use the last day of the year.
- If Day, Month and year are all missing, assign ‘continuing’ status to stop date

8 STATISTICAL METHODS

8.1 General statistical conventions

All statistical procedures will be completed using SAS version 9.3 or higher.

The statistical analysis of the first treatment cycle and the open label extension phase (cycles 2-4) will be performed after database lock of all data up to the end of the study (can take place in four-weekly intervals from study week 48 until study week 60) and final unblinding.

The statistical testing of the primary endpoint as well as the key secondary endpoints will be one-sided and will be performed using a significance (alpha) level of 0.025. A two-sided McNemar test (using a significance level of 0.05) will be used to compare the response proportions between week 4 re-treatment visit and at the preceding end of the cycle visit. This endpoint will be separately analyzed for each open label extension cycle. Two-sided 95% CIs will be provided when relevant.

Continuous variables will be summarized using descriptive statistics, including number of subjects (n), mean, standard deviation (SD), median, minimum and maximum. One additional decimal point for mean and median and two additional decimal points for SD will be used in addition to the number of decimal points used for the measured values.

For categorical variables, summaries will include counts of subjects and percentages in corresponding categories. Percentages will be rounded to one decimal place.

For statistical analyses “baseline” refers to the last observation before treatment, i.e. pre-treatment values measured on the treatment day (baseline visit, day 0), and if missing or not evaluated, values from screening visit will be used.

All summaries will be presented by treatment group, unless otherwise specified.

Analyses will be performed by visit, irrespective of any time window deviations.

All subject data, including those derived, will be presented in individual subject data listings. Unless otherwise stated, unscheduled visit results will be included in date/time chronological order, within patient listings only. All listings will be sorted by investigational site, patient number, date/time and visit. The treatment group will be stated on each listing. Unless otherwise stated, data listings will be based on the Safety Analysis Set. A listing with demographic data for screening failures will be presented.

Statistical Analysis Plan (SAP)

8.2 Subject disposition

Subject disposition information will be summarized for the double-blind phase by treatment group and overall as well as separately for the open label phase. The number and percent of subjects who are randomized, who obtained a dose of study drug, who were randomized and not treated, who were treated and not randomized, who complete the double-blind treatment phase, who complete the study and who withdraw early from the study will be presented.

The primary reason for early withdrawal will also be tabulated.

Subject disposition will be listed.

The number and percent of subjects in each analysis set will also be tabulated.

Treatment Misallocations:

If a subject was:

- Randomized but not treated, then they will be reported under their randomized treatment group for efficacy analyses. However, they are by definition excluded from the safety analyses as actual treatment is missing.
- Treated but not randomized, then by definition they will be excluded from the efficacy analyses since they are not randomized but will be included in safety analyses.
- Randomized but got incorrect treatment, then they will be reported under their randomized treatment group for all efficacy analysis, but will be reported under the treatment they actually received for all safety analyses.
- Patients who were not treated as randomized will be excluded from the per-protocol analysis.

8.3 Protocol deviations

The number of patients excluded from SAF, FAS, MFAS, and PP and reasons for exclusion will be summarized by treatment group and overall.

Analysis set membership details will be listed, including reason for exclusion from each analysis set.

All major protocol deviations identified will be summarized by treatment group and overall. Minor protocol deviations will be listed only.

A listing will include the inclusion/exclusion criteria violated at Screening and at Re-treatment on cycles 2, 3 and 4 as well as other protocol deviations identified based on data

Statistical Analysis Plan (SAP)

recorded on the electronic case report form (eCRF) and/or protocol deviation Logs from [REDACTED] (based on the Safety Analysis Set).

8.4 Demographics and baseline characteristics

8.4.1 Demographics

Age, sex, race, ethnicity, height, weight, body mass index, and Fitzpatrick skin type at baseline will be summarized descriptively by treatment group and overall using the FAS Population. The FDA guideline regarding “Collection of race and ethnicity data in clinical trials” will be followed.

8.4.2 Baseline characteristics

The categorical baseline characteristics such as baseline ECG, pregnancy test results and antibody test sample collection (yes/no) at screening will be summarized using frequency counts for the FAS Population. Continuous baseline variables such as systolic blood pressure (mmHg), diastolic blood pressure (mmHg) and pulse rate (beats/min) will be summarised by descriptive statistics in the same way as continuous demographic variables for the FAS Population.

8.4.3 Medical history

A summary of medical history will be presented by system organ class (SOC) and preferred term (PT) using Medical Dictionary for Regulatory Activities® (MedDRA) Version 19.0 or higher. The previous toxin treatment will be listed only.

8.4.4 Prior and concomitant medications

Medications used in this study will be coded by using the latest available version of the World Health Organization Drug Dictionary Standard or Enhanced and categorized as follows:

Prior medications and concomitant medications will be summarized descriptively using frequency tables by anatomical therapeutic chemical (ATC) class and preferred name by treatment group on the FAS and presented separately for the following groups:

- Medication (recent) discontinued prior to Baseline (Day 0)
- Concomitant medication started at or after Baseline, or started before Baseline and were not discontinued prior to Baseline

Details for imputing missing or partial start and/or stop dates of medication are described in Section 7.2.2.

8.5 Extent of exposure

8.5.1 Duration of study drug exposure

Duration of study drug exposure (in days) will be calculated as date of last study medication administration minus date of first study medication administration + 1 day, regardless of study drug interruption.

Study drug exposure will be summarised by treatment group and separated for the double-blind and open label phase on the Safety Analysis Set using time intervals and summary statistics. Planned and actual dose as well as injections at all sites per subject and treatment cycle will be listed.

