6.3.1 First Treatment Cycle

The first treatment cycle of the study will comprise two treatment groups as follows:

- Group A (active): BoNT/A-DP (20 units, 0.5 mL).
- Group B (placebo control): sterile, 0.9% sodium chloride (0.5 mL).

Eligible subjects will be randomized at baseline (day 0) to Group A or B to receive the first treatment in a 3:1 randomization scheme, respectively. Investigators and subjects will be blinded to the treatment administered and will evaluate the severity of glabellar lines independently. The subjects must perform their assessment independently and ideally before the investigator, to ensure they are not biased by the investigator. The same investigator must assess the subject at baseline and at the visits at weeks 1, 2 and 4 in the first treatment cycle.

After a screening period of up to 14 calendar days, subjects will receive the first treatment (BoNT/A-DP or placebo) and attend for visits at 1, 2 and 4 weeks after treatment and at 4-weekly intervals thereafter for evaluation of efficacy and safety (primary and key secondary efficacy endpoints will only be evaluated in the first treatment cycle in comparison with placebo). Re-screening will not be permitted.

The effect of botulinum toxin typically lasts a few months, hence the first treatment cycle will last at least 12 weeks and will end when the subjects qualify for re-treatment (in accordance with the "eligibility for re-treatment criteria" as outlined in Section 7.3). Efficacy duration of four to six months³⁶ or 17.1 ± 6.5 weeks³⁵ have been reported from other studies, hence the study is designed flexibly to adequately assess the duration of effect compared with placebo in the first treatment cycle.

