If at an Evaluation for Re-treatment visit the subject wants to get re-treated, but the investigator does not agree or vice versa (i.e. the FWS score is not \geq at least 2 by both assessments), the subject will return to the site 4 weeks thereafter for another Evaluation for Re-treatment visit. There is no limit to the number of Evaluation for Re-treatment visits. In order to consider a visit as the End of Cycle visit, there must always be agreement between investigator and subject on a FWS score (at maximum frown) of ≥ 2 .

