3.1 General study design

This multicenter Phase 3 study is comprised of two parts. The first part of the study is a randomized, double blind, placebo-controlled, phase which aims to demonstrate efficacy and safety of BoNT/A-DP compared with placebo. The second part is an open label extension phase to evaluate efficacy after repeat treatments and long term safety.

Subjects can receive a maximum of four treatment cycles over the duration of the study, a single treatment in the first cycle compared with placebo, and up to three subsequent treatments in the open label extension study.

Adult subjects less or equal 75 years old with moderate to severe glabellar frown lines at maximum frown with an important psychological impact as indicated by scores >0 on either the Emotional or Functioning subscales of the modified Skindex-16 (GL-QoL) will be enrolled in this study. Approximately 18 sites (50% in EU and 50% in US) will enroll in total 700 evaluable subjects. Applying a 10% drop out rate will result in a total number of completing subjects of about 630.

The overall study scheme is presented below:

[figure not shown]

The duration of study participation for each subject will be up to 14 calendar days of screening followed by 48 to 60 weeks of treatment (re-screening will not be permitted). The first treatment cycle will be a double blinded cycle followed by up to three open label treatment cycles. Each cycle will be at least 12 weeks and can be prolonged in 4-week increments, depending on treatment effect. Re-treatment is possible until study-week 48.

[figure not shown]
Statistical Analysis Plan (SAP)

Visit Scheme/Treatment Cycle 1 (double blind)

Visit Scheme/Treatment Cycles 2, 3, 4 (open label)

Statistical Analysis Plan (SAP)

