7 STATISTICAL CONSIDERATIONS AND ANALYSIS

7.1 Derived Variables

The below, table provide the list of derived variables for various duration derivations and baseline derivations applicable for this study.

Variables	Formula
Derivation of Duration	
Study day at any visit	Date of interest – date of first dose of study drug.
Extent of Exposure (Days)	Date of last study medication administration – Date of first study medication administration + 1
Extent of Exposure (Weeks)	Extent of exposure (days)/7
Baseline Derivations	
Baseline	The baseline value is defined as the last observation before treatment, i.e. pre-treatment values measured on the treatment day (baseline visit, day 0), and if missing or not evaluated, the value from screening visit.
Change from baseline	Post baseline value – Baseline value
Relative change from baseline	[(Post baseline value – Baseline value)/Baseline value]*100

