8.7.1 Treatment Exposure

A summary table displaying the number of subjects by the number of treatment cycles will be prepared. The duration of study drug exposure (calculated as described in section 8.5.1) during each treatment cycle will be analyzed by summary statistics.

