8.7.2 Adverse events (secondary safety endpoint 1)

All AEs will be classified by SOC and PT according to MedDRA Version 19.0 or higher.

In summaries by SOC and PT, adverse events will be sorted by decreasing frequency within each SOC and PT. In summaries by PT, AEs will be sorted by decreasing frequency within each PT.

AE summary tables will be presented for TEAEs and AESIs separately by treatment cycle and will include the number and percentage of subjects with any:

- TEAE/AESI
- TEAE/AESI related to study medication (AE will be defined as related if causality is definitely, probably or possibly or if causality assessment is missing)
- TEAE/AESI related to injection procedure (AE will be defined as related if causality is definitely, probably or possibly or if causality assessment is missing)
- Severe TEAE/AESI

Statistical Analysis Plan (SAP)

- Severe TEAE/AESI related to study medication
- Severe TEAE/AESI related to injection procedure
- TEAE/AESI leading to discontinuation
- Study drug related TEAE/AESI leading to discontinuation
- Serious TEAE/AESI
- TEAE/AESI leading to death.

All TEAEs as well as all AESIs will be summarized by SOC, PT and treatment group using frequency counts and percentages (i.e. number and percentage of subjects with an event).

The number of events, as well as the number and rate of affected subjects will be reported by SOC and PT for all TEAEs and for all AESIs separately.

Adverse events will be separated to pre-treatment AEs and TEAEs. TEAEs are defined as all AEs with onset or worsening (increase in severity) after receiving first dose of study medication (independent of whether it is BoNT/A-DP or placebo). If it cannot be determined whether an AE is treatment-emergent due to a partial onset date, then it will be counted as such.

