TEAEs and AESIs will be analyzed overall (for BoNT/A-DP or placebo), and for BoNT/A-DP treatment group additionally separately per first treatment cycle or open label extension phase: events starting on or after first treatment up to before open label extension (first cycle), and events starting on or after re-treatment until end of study (open label phase). If it cannot be determined whether an AE started during the first treatment cycle or the open label extension phase due to a partial onset date, then it will be counted as having started during first treatment cycle. The assignment of AEs to the different cycles of the open label extension phase will be done similarly: AEs will be assigned to a certain cycle if they start on or after treatment of the respective cycle but before treatment of the next cycle. In case that there is no subsequent treatment cycle, all AEs (starting on or after the last treatment) until end of study will be assigned to the last cycle.

Events of subjects who started the first treatment with placebo but then entered the open label extension for re-treatment with BoNT/A-DP will be considered to placebo for the first cycle and to BoNT/A-DP for the open label phase.

TEAEs and AESIs (per SOC and PT) will also be summarized by seriousness, severity, relationship to study medication, and relationship to procedure using frequency counts and percentages (i.e. number and percentage of subjects with an event).

Statistical Analysis Plan (SAP)

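### The SAP exposure formula gives 1 day for every subject in the double-blind phase and in each cycle, so follow-up by arm is never shown beside the crude cycle 1 adverse event percentages

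*SAP*

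**What the plan says.** SAP 7.1 (Derived Variables) defines extent of exposure in days as "Date of last study medication administration – Date of first study medication administration + 1". SAP 8.5.1 repeats the definition ("calculated as date of last study medication administration minus date of first study medication administration + 1 day") and summarises the result by treatment group, separately for the double-blind and open-label phases. SAP 8.7.1 carries it to a finer level: "The duration of study drug exposure (calculated as described in section 8.5.1) during each treatment cycle will be analyzed by summary statistics".

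SAP 3.1 describes the dosing as "a single treatment in the first cycle compared with placebo", then up to three open-label treatments, one opening each later cycle.

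Protocol 6.3.1 states that "the first treatment cycle will last at least 12 weeks and will end when the subjects qualify for re-treatment". Under Protocol 6.3.2 a cycle closes only when investigator and subject both score FWS at maximum frown at 2 or more. Evaluations start at week 12 and repeat every 4 weeks, and the last re-treatment is at week 48.

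For safety, SAP 8.7.2 says: "All TEAEs as well as all AESIs will be summarized by SOC, PT and treatment group using frequency counts and percentages". Event counts are added. Cycle 1 events are those starting from the first injection up to the start of the open-label phase. No rate per unit of follow-up is planned.

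**The concern.** With one administration per cycle, the first and last administration dates within a cycle are the same. The formula then returns a constant, and the planned time-interval tables and summary statistics carry no information. When cycles are pooled the value does vary, but it leaves out all follow-up after the last injection.

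This matters because cycle 1 length depends on outcome. Subjects enter with FWS 2 or 3 by both raters (Protocol 7.1), so a placebo subject with no change meets the FWS condition for re-treatment at week 12. A subject whose effect persists stays in cycle 1 and keeps accruing adverse events to it. Without follow-up by arm, the cycle 1 adverse event table does not let a reader separate a drug effect from longer observation. Long-term safety data and a safety database for approval are stated objectives (SAP 2.2, item 3).

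**Working it through.** **The formula within a cycle or the double-blind phase.** Last date = first date, so exposure = 0 + 1 = 1 day. The formula was applied to all 59 nominal schedules the protocol allows (week 0, then 0 to 3 re-treatments on the 4-weekly grid from week 12 to week 48, at least 12 weeks apart):

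| Level | SAP formula (days) |
|---|---|
| Double-blind phase, either arm | 1 in all 59 |
| Any single cycle | 1 in all 59 |
| Open-label phase, one re-treatment | 1 |
| Open-label phase, two re-treatments | 85 to 253 |
| Open-label phase, three re-treatments | 169 to 253 |
| Whole study | 1 to 337 |

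Actual cycle 1 length in the same schedules is 12 × 7 = 84 to 48 × 7 = 336 days. The 1-day value would apply to all 700 planned subjects, apart from a deviation with two injection dates in one cycle.

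**Pooled cycles.** Treatments at weeks 0, 12, 24 and 36 give 36 × 7 + 1 = 253 days, against 48 × 7 = 336 days to End of Study at week 48. The open-label part gives 24 × 7 + 1 = 169, against 36 × 7 = 252.

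**What unequal follow-up could do to crude percentages.** This is an illustration with the same hazard in both arms. Inputs and assumptions:
- 28.4% of BoNT/A-DP subjects with an adverse event in the earlier Korean glabellar line study (Protocol 4.4.2.1), over 16 weeks (Protocol Table 4-2).
- 60% and 10% responders from the sample size section, used as a proxy for staying past week 12; everyone else leaves at week 12.
- Duration of effect for those staying: Normal with mean 12.1 or 17.1 weeks (Protocol 4.5.1.2), or 21.7 weeks (the midpoint of the four to six months cited there), SD 6.5 weeks throughout. They leave at the first 4-weekly visit at or after that time, at week 48 at the latest.

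Constant hazard: h = −ln(1 − 0.284)/16 = 0.0209 per week, and the crude proportion over w weeks is 1 − exp(−h·w). This gives 22.2% at 12 weeks, 28.4% at 16 and 39.4% at 24. Averaging over the assumed cycle lengths:

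| Mean duration of effect | Mean cycle 1 length, active vs placebo | Crude %, active vs placebo | Excess (points) |
|---|---|---|---|
| 12.1 weeks | 14.2 vs 12.4 weeks | 25.5 vs 22.7 | 2.8 |
| 17.1 weeks | 16.5 vs 12.8 weeks | 28.7 vs 23.2 | 5.4 |
| 21.7 weeks | 19.1 vs 13.2 weeks | 32.0 vs 23.8 | 8.2 |

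(Excesses are computed before rounding.)

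If events cluster after injection, the effect shrinks. With an exponentially decaying hazard rescaled to 28.4% at 16 weeks, the excess is 1.3, 2.3 and 3.3 points for a half-life of 8 weeks, and 0.5, 0.9 and 1.2 points for a half-life of 4 weeks.

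**The case against.** The 1-day arithmetic is not in dispute. The case on the other side concerns its consequences.

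- *Other planned outputs give clues.* SAP 8.6.3 describes cycle 1 visits after week 20 up to week 48 and excludes subjects already re-treated, so the number per visit hints at who remains. SAP 8.7.1 counts subjects by number of cycles, a sensible exposure measure for a product given in single sessions. SAP 8.7.2 tabulates events by relationship to study drug and to procedure. Injections are listed per subject. Protocol 12.4.3 promises detailed tabulation of exposure. All of this is true, but none of it summarises time at risk by arm. The late-visit numbers miss re-treatment at weeks 12 to 20, and the protocol sentence has no formula.
- *The illustration uses weak proxies.* The week 4 responder definition is not the exit rule: one rater scoring below 2 is enough to stay. Placebo responders are given the toxin's duration of effect. The SD of 6.5 belongs only to the 17.1-week figure, and 12.1 weeks is a median. Using 9.0%, the treatment-related proportion in the same earlier study, the excess is 1.0, 2.0 and 3.1 points with a constant hazard and 0.2 to 0.4 points with a 4-week half-life. This stands as a limit on the size, which is why a range is given; the formula defect does not depend on it.
- *Crude percentages by cycle are clearly specified and agree with the protocol.* Also true. The extra adverse event tables supplement them and do not correct a contradiction.
- *The bias is conservative, safety is descriptive with no test, and efficacy is untouched.* This stands, and it limits the seriousness of the point.

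**Conclusion.** The concern holds. As written, the SAP formula yields 1 day for every treated subject in cycle 1 and in each open-label cycle, against 84 to 336 days of cycle 1 follow-up for those who complete it. SAP section 9 lists no change that would correct this. This part follows from the SAP text and needs no assumption.

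That follow-up will differ by arm is an expectation from the exit rule; the documents give no figure. With no drug effect, the resulting excess in the active arm's crude percentage is 0.5 to 8.2 points under the assumptions listed, and smaller if only treatment-related events are counted. It would overstate active risk rather than hide it. The point should be corrected before the SAP is final, but it does not threaten the efficacy conclusion.

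**What to change.** In SAP 7.1, 8.5.1 and 8.7.1, define follow-up for each cycle as the date of the next injection, or of End of Study or last contact if there is none, minus the date of that cycle's injection. Summarise it by arm for cycle 1 and by cycle in the open-label phase. Keep the table of subjects by number of cycles.

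In SAP 8.7.2, add two outputs by arm: TEAEs and AESIs in the first 12 weeks after the first injection, and exposure-adjusted rates for the whole of cycle 1.

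The cost is revised SAP wording and a few more tables, all from dates already collected. The safety output grows, and the 12-week table omits later cycle 1 events, so the full-cycle table must stay beside it.
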